5.5.9 Emergency breaking of assigned treatment code

Emergency treatment code breaks should only be undertaken when it is essential to treat the patient safely and efficaciously. Most often, study drug discontinuation and knowledge of the possible treatment assignments are sufficient to treat a study patient who presents with an emergency condition. Emergency treatment code breaks are performed using the IRT. When

the investigator contacts the system to break a treatment code for a patient, he/she must provide the requested patient identifying information and confirm the necessity to break the treatment code for the patient. The investigator will then receive details of the investigational drug treatment for the specified patient and a fax or email confirming this information. The system will automatically inform the Novartis monitor for the site and the Study Lead or designee that the code has been broken.

It is the investigator's responsibility to ensure that there is a dependable procedure in place to allow access to IRT at any time in case of emergency. The investigator will provide:

- protocol number
- study drug name (if available)
- patient number

In addition, oral and written information to the subject must be provided on how to contact his/her backup in cases of emergency, or when he/she is unavailable, to ensure that unblinding can be performed at any time.

An assessment will be done by the appropriate site personnel and the Medical Lead (or designee) after an emergency treatment code break and the patient must discontinue the study treatment.

5.6 Study completion and discontinuation

5.6.1 Study completion and post-study treatment

A patient will be considered to have completed the study when the patient has completed the last visit planned in the protocol. The study will be completed when the last patient enrolled has completed their last visit (24 weeks after randomization). Patients will continue to be followed in the study regardless of study drug discontinuation.

The investigator must provide follow-up medical care for all patients who are prematurely withdrawn from study drug, or must refer them for appropriate ongoing care. An open-label extension study may be available through the sponsor dependent on the results of the PARAGON-HF study.

5.6.2 Discontinuation of study treatment

Patients may voluntarily discontinue study treatment for any reason at any time. However, study treatment discontinuation does not constitute withdrawal from the study, does not constitute withdrawal of consent and should not lead to the patient being withdrawn from the study. Patients who have discontinued study drug should be encouraged to attend all the protocol specified study visits and perform all measurements as stipulated in the visit schedule ([Table 6-1](#)) and remain in follow up for the duration of the trial.

If they fail to return for these assessments for unknown reasons, every effort should be made to contact them. The investigator must also contact the IRT to register the patient's interruption from study treatment and record it on the Dosage Administration Record.

If the patient does not attend the study visits, follow-up should continue according to the specified schedule by telephone to determine if any AEs pre-specified in the protocol have

occurred, except in the case that the patient **specifically** refuses such follow-up and withdraws his/her consent.

The emergence of the following circumstances will require permanent study drug discontinuation:

- Withdrawal of informed consent
- Investigator thinks that continuation would be detrimental to the patient's well-being
- Suspected occurrence of angioedema ([Section 6.5.7](#)). A patient with any signs or symptoms of clinically significant angioedema should be thoroughly evaluated by the investigator
- Pregnancy and post-pregnancy during lactation period ([Section 6.5.6](#) and [Section 7.6](#))

The emergence of the following circumstances will require temporary or permanent discontinuation (study drug may be restarted once these circumstances no longer exist):

- Use of an open label ACE inhibitor, ARB, or renin inhibitor ([Section 5.5.8](#))
- Any laboratory abnormalities that in the judgment of the investigator warrant discontinuation of study drug after taking into consideration the patient's overall status ([Section 6.5.4](#))

Study drug may be discontinued at the investigator's discretion if any of the following occurs:

- Any severe suspected drug-related AE ([Section 7.1](#))
- Any other protocol deviation that results in a significant risk to the patient's safety

The appropriate personnel from the site and Novartis will assess whether study drug should be permanently discontinued for any patient whose treatment code has been broken inadvertently for any reason.

5.6.3 Withdrawal of informed consent

Subjects may voluntarily withdraw consent to participate in the study for any reason at any time. Withdrawal of consent occurs only when a subject:

[figure not shown]
- Does not want to participate in the study anymore, and
- Does not allow further collection of personal data

In this situation, the investigator must make a reasonable effort (e.g. telephone, e-mail, letter) to understand the primary reason for the subject's decision to withdraw his/her consent and record this information.

Study treatment must be discontinued and no further assessments conducted, and the data that would have been collected at subsequent visits will be considered missing.

Further attempts to contact the subject are not allowed unless safety findings require communicating or follow-up.

All efforts should be made to complete the assessments prior to study withdrawal. A final evaluation at the time of the subject's study withdrawal should be made as detailed in the assessment table.

Novartis will continue to keep and use collected study information (including any data resulting from the analysis of a subject's samples until their time of withdrawal) according to applicable law.

For US and Japan: All biological samples not yet analyzed at the time of withdrawal may still be used for further testing/analysis in accordance with the terms of this protocol and of the informed consent form.

For EU and Rest of the World (RoW): All biological samples not yet analyzed at the time of withdrawal will no longer be used, unless permitted by applicable law. They will be stored according to applicable legal requirements.

5.6.4 Loss to follow-up

For patients whose status is unclear because they fail to appear for study visits without stating an intention to discontinue or withdraw, the investigator must show "due diligence" by documenting in the source documents steps taken to contact the subject, e.g. dates of telephone calls, registered letters, etc. A patient cannot be considered as lost to follow-up until the time point of his/her scheduled end of study (EOS) visit has passed.

5.6.5 Early study termination by the sponsor

The study can be terminated by Novartis at any time for any reason. This may include reasons related to the benefit risk assessment of participating in the study, practical reasons, or for regulatory or medical reasons (including slow enrolment). Should this be necessary, the patient must be seen as soon as possible and treated as a prematurely withdrawn patient. The investigator may be informed of additional procedures to be followed in order to ensure that adequate consideration is given to the protection of the patient's interests. The investigator will be responsible for informing the Institutional Review Board/Independent Ethics Committee (IRBs/IECs) of the early termination of the trial.

6 Visit schedule and assessments

[Table 6-1](#) lists all of the assessments and indicates with an "x" when the visits are performed.

Patients must be seen for all visits on the designated day, or as close to it as possible. Missed or rescheduled visits should not lead to automatic discontinuation. Patients who prematurely discontinue the study for any reason should be scheduled for a visit as soon as possible, at which time all of the assessments listed for the final visit will be performed. At this final visit, all dispensed investigational treatment should be reconciled; all the AEs and concomitant medications also should be reconciled on the eCRFs.

Patients who have discontinued study drug should be encouraged to attend all the protocol specified study visits and perform all measurements as stipulated in the visit schedule ([Table 6-1](#)) and remain in follow up for the duration of the trial. Visit 101 will be considered the reference visit for all study visits during the treatment epoch. Regardless of the occurrence of any unscheduled visits, scheduled visits should be performed within the specified timeframe in relation to Visit 101 as outlined in [Table 6-1](#). If a visit is completed earlier than scheduled or postponed, it should not result in the next visit being brought forward or postponed.

[figure not shown]

Table 6-1 Assessment schedule

Epoch	Screen	Double-blind treatment							
Visit	1	101	102	103	104	105	106	107	199 and/or PSD
Week(w)	-2	0	2	4	8	12	16	20	24
Day	-14	1	14	28	56	84	112	140	168
Obtain informed consent*	X								
Inclusion/exclusion criteria	X	S							
Medical history/demography	X								
Heart failure and diabetes history	X								
Cardiovascular medical history	X								
Concomitant medications	X	X	X	X	X	X	X	X	X
Alcohol & smoking history	X								
Complete physical exam	S								S
Short physical exam		S	S	S	S	S	S	S	
Vital signs (BP and pulse)	X	X	X	X	X	X	X	X	X
Height	X								
Weight	X	X	X	X	X	X	X	X	X
Waist/hip circumference	X					X			X
12-lead ECG assessment	X					X			X
Echocardiography ¹	X								
NYHA classification (HF signs/symptoms)	X	X	X	X	X	X	X	X	X
KCCQ questionnaire	X	X		X		X	X		X
Six-minute walk test	X	X					X		X
SF-36		X					X		X

[figure not shown]
Epoch	Screen	Double-blind treatment							
Visit	1	101	102	103	104	105	106	107	199 and/or PSD
Week(w)	-2	0	2	4	8	12	16	20	24
Management of comorbidities (Blood Pressure)	x	x	x	x	x	x	x	x	x
Management of comorbidities (Diabetes, Lipids)	x	x				x			x
Management of comorbidities (Arrhythmias)	x					x			x
Complete laboratory evaluations ²	X	X				X			X
Abbreviated laboratory evaluations ³			X	X	X		X	X	
FSH ⁴	X								
Serum/urine pregnancy test ⁵	X	X	X	X	X	X	X	X	X
Plasma NT-proBNP ⁶	X	X		X		X			X
AEs/SAEs		X	X	X	X	X	X	X	X
Contact IRT	X	X	X	X	X	X	X	X	X
Dispense study medication		X	X	X	X	X	X	X	
Screening disposition	X								
Treatment compliance			X	X	X	X	X	X	X
Treatment disposition									X
Study completion form									X

PSD = Premature Subject Discontinuation

X = assessment to be recorded on clinical data base

S = assessment to be recorded on source documentation only

*IC obtained prior to all study specific screening procedures

¹ Qualifying LVEF measurements/documentation of structural heart disease will be based on locally obtained echocardiograms (echo) performed within 6 months of Visit 1. If a locally performed echo within 6 months of Visit 1 is not available, an echo must be performed during the screening epoch.

[figure not shown]
² Complete laboratory evaluations including urinalysis will be sent to the central lab at all specified visits.

³ Abbreviated laboratory evaluations will be sent to the central lab and include: BUN, creatinine, potassium, and eGFR, and may additionally be performed in the local lab as needed and include: creatinine, potassium, and eGFR. Lab results must be available and assessed before any study drug up-titration (see [table 3-3](#))

⁴ Not required for males or pre-menopausal women.

⁵ Not required for males or post-menopausal women. Serum pregnancy test performed at Visit 1 and 199/PSD. Urine pregnancy test performed at all other study visits.

⁶ Only the Visit 1 NT-proBNP results will be reported to the investigator and the sponsor. Local measurements of BNP or NT-proBNP during the course of the study is strongly discouraged.

6.1 Information to be collected on screening failures

All patients who have signed informed consent but not entered into the next epoch will have the study completion page for the screening epoch, demographics, inclusion/exclusion, and SAE data collected. Adverse events that are not SAEs will be followed by the investigator and collected only in the source data.

Re-screening

A patient who enters screening but is determined not to be eligible will be considered a screen failure. The investigator may consider re-screening the patient at a later time if he/she believes that the patient's condition has changed and they may potentially be eligible. In this case, a new patient number will be allocated to the subject and he/she will need to re-perform all Visit 1 procedures. A patient may be re-screened once. A minimum of 2 weeks must elapse between screen failure and re-screening. The patient must provide new written informed consent before they are re-screened.

6.2 Patient demographics/other baseline characteristics

Patient demographic and baseline characteristic data to be collected on all patients include: year of birth, age, sex, race, ethnicity and source of patient referral. A detailed medical history (including HF, CV and other conditions relevant to the study population to be enrolled) and current medical conditions present before the signing of the informed consent will be collected.

Investigators will have the discretion to record abnormal test findings on the medical history eCRF whenever in their judgment, the test abnormality occurred prior to the informed consent signature.

6.3 Treatment exposure and compliance

[figure not shown]
Compliance will be assessed by the investigator and/or study personnel at each visit using pill counts and information provided by the patient or care giver. This information should be captured in the Study Treatment Compliance eCRF at each visit. The investigator and/or study personnel should counsel the patient if compliance is below 80% at any time during the study. Study drug accountability will be determined by the site monitor while performing routine site visits and at the completion of the study. All study treatment dispensed and returned must be recorded in the Drug Accountability Log.

The duration of randomized treatment exposure will be calculated based upon the start and stop dates recorded in the Dosage Administration Record eCRFs.

6.4 Efficacy

6.4.1 Primary efficacy assessment

The primary efficacy variables are change from baseline in NT-proBNP (in log scale) at Week 12 and change from baseline in six-minute walk distance (6MWD) at Week 24.

6.4.2 Secondary efficacy assessment

The secondary efficacy variables include:

- KCCQ CSS at Week 24
- NYHA functional classification at Week 24
- SF-36 PCS score at Week 24

6.4.3 Appropriateness of efficacy assessments

Rationale for the choice of endpoints for the study has been outlined previously ([Section 3.2.2](#) and [3.2.3](#)). The primary efficacy assessments, NT-proBNP and 6MWT, are key clinical measures in this patient population for response to therapy, exercise capacity improvement and assessment of overall risk. The secondary efficacy assessments (KCCQ, SF-36 and NYHA) are validated measures of symptoms and quality of life in patients with HFpEF.

6.5 Safety

Novartis may request additional information on specific AEs or laboratory events of interest and may make requests to perform additional diagnostic tests to further assess the safety profile of the study drugs. Such information may include diagnostic procedure reports, discharge summaries, autopsy reports, and other relevant information that may help in assessing the reported AE. All additional information will be de-identified prior to collection by Novartis or its agents.

6.5.1 Physical examination

A complete physical examination will include the examination of general appearance, skin, neck (including thyroid), eyes, ears, nose, throat, lungs, heart, abdomen, back, lymph nodes, extremities, vascular and neurological. If indicated based on medical history and/or symptoms, rectal, external genitalia, breast, and pelvic exams will be performed. Complete physical examination will be performed at Visit 1 and 199/PSD.

A short physical exam will include the examination of general appearance and vital signs (BP [SBP and DBP] and pulse). A short physical exam will be conducted at all visits starting from Visit 101 except where a complete physical examination is required (see [Table 6-1](#)).

Information from all physical examinations must be included in the source documentation at the study site. Significant findings that are present prior to signing informed consent must be included in the Medical History part of the eCRF. Significant findings made after signing the informed consent which meet the definition of an AE must be recorded on the AE section of the eCRF.

6.5.2 Vital signs

Vital signs include BP and pulse measurements. BP will be measured in the sitting position after 5 minutes of rest using an automated validated device (eg OMRON) or a standard sphygmomanometer with an appropriately sized cuff on the non-dominant arm. Vital signs will be performed at each study visit.

6.5.3 Height, weight and waist/hip circumference

Height in centimeters (cm) will be measured at Visit 1. Body weight (to the nearest 0.1 kilogram [kg] in indoor clothing, but without shoes) will be measured at each study visit.

Waist/hip circumference (to the nearest centimeter [cm] in indoor clothing) will be measured at Visit 1, 105, and 199/PSD.

6.5.4 Laboratory evaluations

A central laboratory will be used for analysis of all specimens collected. Details on the collection, shipment of samples and reporting of results by the central laboratory are provided to investigators in the laboratory manual.

Clinically notable laboratory findings are defined in [Appendix 1](#).

Complete laboratory evaluations such as hematology and blood chemistry ([Table 6-2](#)) for the assessment of safety in this study will be performed at Visits 1, 101, 105 and 199/PSD.

Abbreviated laboratory evaluations will be performed as indicated in [Table 6-1](#). Abbreviated central laboratory includes: BUN, creatinine, potassium, and eGFR.

In addition to the required central laboratory assessments, a local laboratory may be used for the assessment of creatinine, potassium and eGFR during the up-titration period as indicated in [Table 6-1](#). The results from the local laboratory during the up-titration period will be allowed to be used for decision making regarding the eligibility of the patient to continue on in the study and will be recorded on the appropriate eCRF. In addition, local laboratory assessments may be performed on an as-needed basis to monitor tolerability to study drug at unscheduled visits during the randomized treatment period and will be recorded in the appropriate eCRF.

Laboratory values that exceed the boundaries of a notable laboratory abnormality ([Appendix 1](#)) must be commented on by the investigator in the patient's eCRF and additional laboratory evaluations should be performed, as judged appropriate by the investigator. If the laboratory abnormality induces clinical signs or symptoms, or requires therapeutic intervention, then the diagnosis or medical condition must be entered on the AE eCRF. If the laboratory abnormality is the primary reason for an unforeseen hospitalization or otherwise fulfills the seriousness category of an AE, then the procedure for rapid notification of SAEs must be followed. If the laboratory abnormality leads to study drug discontinuation (temporarily or permanently), the patient must be followed until the abnormality resolves or until it is judged to be permanent. The investigation may include continued monitoring by repeat laboratory testing or by performing additional laboratory tests as deemed necessary by the investigator or the Novartis medical monitor.

All central laboratory results will be communicated to the investigators and the sponsor, with the exception of NT-proBNP of which only the Visit 1 NT-proBNP will be reported ([Section 6.6.1.4](#)).

Table 6-2 Complete laboratory evaluations

Hematology	Biochemistry	Urine measurements
Hematocrit	Alanine aminotransferase (ALT)	Urinalysis
Hemoglobin	Albumin (Alb)	
Platelet count	Alkaline phosphatase (ALP)	
Red blood cell count (RBC)	Aspartate aminotransferase (AST)	
White blood cell count (WBC)	Blood urea nitrogen (BUN)*	
WBC differential	Calcium	
Red blood cell distribution width (RDW)	Chloride	
Mean corpuscular volume (MCV)	Creatinine*	
Mean corpuscular hemoglobin concentration (MCHC)	eGFR*	
	Glucose	
	Hemoglobin A1C	
	Lipid profile (total cholesterol, LDL, HDL, and triglycerides)	
	Phosphate	
	Potassium*	
	Serum pregnancy test	
	Sodium	
	Total bilirubin (TBL)	
	Fractionated bilirubin (if total bilirubin > 2 x ULN)	
	Total protein	
	Uric acid	

*Laboratory assessments for the abbreviated laboratory evaluation at visits where the complete laboratory evaluation is not performed

6.5.4.1 Hematology

Hemoglobin, hematocrit, RBC, RDW, MCHC, MCV, WBC with differential, and platelet count will be measured.

6.5.4.2 Clinical chemistry

Blood urea nitrogen (BUN), creatinine, total bilirubin (TBL), fractionated bilirubin (if total bilirubin > 2 x ULN), AST, ALT, alkaline phosphatase, sodium, glucose (plasma), hemoglobin A1C, lipid profile, potassium, phosphate, chloride, calcium, total protein, albumin, and uric acid will be measured. Potassium, BUN, creatinine, and eGFR will be obtained at study visits where abbreviated central laboratory evaluations are scheduled.

6.5.4.3 eGFR

Estimated eGFR will be calculated by the central or local laboratory using the following MDRD formula (Stevens et al 2006):

Estimated GFR (mL/min/1.73 m²) = 175 × (standardized SCr in mg/dL)^{-1.154} × (age in years)^{-0.203} × (0.742 if female) × (1.212 if black), where SCr is the standardized serum creatinine value.

6.5.4.4 Urinalysis

Urinalysis with dipstick measurements for specific gravity, pH, total protein, bilirubin, ketones, leukocytes and blood will be performed by central lab. If a dipstick is positive, a qualitative microscopic determination, of WBC and RBC sediments will also be measured.

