7.4 Renal safety monitoring

The following two categories of abnormal renal laboratory values have to be considered during the course of the study:

- Serum event:
 - Serum events are outlined in detail in [Appendix 3](#); surveillance situation (decrease in eGFR $\geq 25\%$ from randomization) and action situation (decrease in eGFR $\geq 40\%$ from randomization) are described
- Urine event
 - new onset ($\geq 1+$) proteinuria; confirmed by doubling in the urinary albumin-creatinine ratio (ACR) or urinary protein-creatinine ratio (PCR) (if applicable)
 - new onset ($\geq 1+$), hematuria or glycosuria

Every renal laboratory trigger or renal event as defined in [Table 15-1](#) in [Appendix 3](#) should be followed up by the investigator or designated personnel at the trial site.

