> 2 × ULN (in the absence of known Gilbert syndrome)	
 Repeat LFT within 48 hours If elevation persists, discontinue the study drug immediately Hospitalize if clinically appropriate Establish causality Complete liver CRF 	ALT, AST, TBL, Alb, PT/INR, ALP and γGT until resolution ^c (frequency at investigator discretion) Test for hemolysis (e.g., reticulocytes, haptoglobin, unconjugated [indirect] bilirubin)
> 1.5 to ≤ 2 × ULN (patient is asymptomatic)	
 Repeat LFT within the next week If elevation is confirmed, initiate close observation of the patient 	Investigator discretion Monitor LFT within 1 to 4 weeks or at next visit
Jaundice	
 Discontinue the study treatment immediately Hospitalize the patient Establish causality Complete liver CRF 	ALT, AST, TBL, Alb, PT/INR, ALP and γGT until resolution ^c (frequency at investigator discretion)
Any AE potentially indicative of a liver toxicity*	
 Consider study treatment interruption or discontinuation Hospitalization if clinically appropriate Establish causality Complete liver CRF 	Investigator discretion

^aElevated ALT/AST > 3 × ULN and TBL > 2 × ULN but without notable increase in ALP to > 2 × ULN
^b(General) malaise, fatigue, abdominal pain, nausea, or vomiting, or rash with eosinophilia
^cResolution is defined as an outcome of one of the following: (1) return to baseline values, (2) stable values at three subsequent monitoring visits at least 2 weeks apart, (3) remain at elevated level after a maximum of 6 months, (4) liver transplantation, and (5) death.

15 Appendix 3: Specific Renal Alert Criteria and Actions

Table 15-1 Specific renal alert criteria and actions

Serum Event	
See detailed guidance below	
Urine Event	
New dipstick proteinuria ≥1+ Albumin- or Protein-creatinine ratio increase ≥ 2-fold	Confirm value after 24 to 48h Perform urine microscopy Consider study treatment interruption / or discontinuation
New dipstick glycosuria ≥1+ not due to diabetes	Blood glucose (fasting) Perform serum creatinine, ACR
New dipstick hematuria ≥1+ not due to trauma	Urine sediment microscopy Perform serum creatinine, ACR
For all renal events:	

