
Document contributing factors in the CRF: co-medication, other co-morbid conditions, and additional diagnostic procedures performed
 
Monitor patient regularly (frequency at investigator's discretion) until either: Event resolution: sCr within 10% of baseline or protein-creatinine ratio within 50% of baseline, or Event stabilization: sCr level with ± 10% variability over last 6 months or protein-creatinine ratio stabilization at a new level with ± 50% variability over last 6 months.
	

Guidelines for the Management of Renal Dysfunction

General principles:

Glomerular filtration rate in HF patients depends on intrinsic renal function and on a balance between afferent and efferent glomerular arterial tonicity. This tonicity is partly regulated by a stimulation of angiotensin II and could be affected by either study drug. Moreover, renal dysfunction may develop or may deteriorate in some patients after study drug administration. These recommendations have been developed to guide the investigators in managing patients with renal dysfunction after randomization.

Two types of response to serum creatinine increase are described:

Surveillance situation

If, at any time after randomization, eGFR decreases by ≥ 25% from randomization (Visit 101) (or if serum creatinine concentration increase to 2.5 mg/dL [221 µmol/L]), the investigator will check for potentially reversible causes of renal dysfunction such as:

- Non-steroidal anti-inflammatory drug intake, antibiotics, or other treatments known to affect creatinine
- Volume decrease, including that resulting from excessive dosing of diuretics
- Urinary infection
- Urinary tract obstruction
- Study drug

Action situation

If a patient's eGFR decreases by $\geq 40\%$ from randomization (Visit 101) (or if serum creatinine concentration rises above 3 mg/dL (265 μ mol/L), the investigator will check for potentially reversible causes of renal dysfunction (see above).

The investigator may consider down-titration of study drugs. If the investigator judges that study drugs have to be stopped, he/she will have to contact the Novartis medical monitor or his/her designee. Thereafter, serum creatinine assessments will have to be repeated at least each week until levels return to acceptable values. If study drug was stopped, every effort will be done to restart it again, according to clinical conditions.

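### New dipstick glycosuria is a renal alert in Section 7.4 and Table 15-1, but the scheduled dipstick in Section 6.5.4.4 has no glucose, so 1 of the 3 urine alerts cannot be triggered as written

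*Protocol*

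**What the plan says.** Protocol Section 6.5.4.4 sets out the urine test: "Urinalysis with dipstick measurements for specific gravity, pH, total protein, bilirubin, ketones, leukocytes and blood will be performed by central lab". It adds microscopy for white and red cells when a dipstick is positive. Table 6-2, and Table 2-10 of the SAP, show a single entry under urine measurements, namely urinalysis. Footnote 2 of Table 6-1 says: "Complete laboratory evaluations including urinalysis will be sent to the central lab at all specified visits". Section 6.5.4 places the complete evaluation at Visits 1, 101, 105 and 199/PSD.

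Section 7.4 describes renal safety monitoring. Its urine events are new proteinuria, plus new "hematuria or glycosuria", each at 1+ or more. Table 15-1 in Appendix 3 has the same three rows. The glycosuria trigger is "New dipstick glycosuria ≥1+ not due to diabetes", and the listed follow-up is a fasting blood glucose and "Perform serum creatinine, ACR". Section 7.4 asks that every trigger or event in Table 15-1 be followed up.

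**The concern.** An alert works only if some planned measurement can set it off. Table 15-1 defines the glycosuria alert by a dipstick reading, but the protocol's list of what the dipstick measures leaves glucose out. Sites following the text would have a written response to a finding that the scheduled testing, as listed, cannot report. Glycosuria would come to light only if an investigator happened to order an extra urine test.

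What is at stake is one safety signal. No efficacy endpoint, eligibility rule, power figure or planned analysis depends on it.

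**Working it through.** This is a comparison of sections. The plan states no figure to reproduce, and the only arithmetic is counting.

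**1. Match each urine alert to a dipstick item.**

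| Urine alert (Section 7.4, Table 15-1) | Item needed | In the Section 6.5.4.4 list? |
|---|---|---|
| Proteinuria | protein | yes |
| Hematuria | blood | yes |
| Glycosuria | glucose | no |

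Alerts defined: 3. Alerts with a listed input: 2. Without one: 3 − 2 = 1.

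**2. Check whether the list is open-ended.** Section 6.5.4.4 names its seven items without presenting them as examples. Where the protocol means a list to be open it says so, as with the antihypertensive drugs in exclusion criterion 11b. The sentence is complete, so neither redaction nor text extraction explains the omission.

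**3. Look for another scheduled source of urine glucose.**
- Tables 6-1 and 6-2 and SAP Table 2-10 go no further than urinalysis.
- Section 6.5.4.2 specifies that the chemistry glucose is plasma glucose.
- Local laboratory use during up-titration (Section 6.5.4) covers creatinine, potassium and eGFR.

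None of these supplies it.

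**4. Count the visits.** Urinalysis is done at 4 visits: 2 pre-dose (1 and 101) and 2 post-baseline (105 and 199/PSD). Visits with a urine glucose result as listed: 0 of 4. Of the 2 post-baseline urinalyses, only Visit 105 (Week 12) is scheduled while study treatment can still be changed. Even a repaired alert would therefore have few chances to alter treatment.

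**5. Check what still works.** Creatinine and eGFR are measured at all 9 visits in Table 6-1: 4 complete plus 5 abbreviated evaluations (102, 103, 104, 106, 107). The rules for an eGFR fall of 25% or 40% from Visit 101 therefore have their inputs. Plasma glucose and HbA1c are drawn at the same 4 visits as the urinalysis. The renal analyses in SAP Table 2-9 use adverse event terms, creatinine and eGFR, with no urine result.

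**6. A side observation on the ratio.** Neither an albumin-creatinine nor a protein-creatinine ratio is scheduled at any of the 9 visits, although Section 7.4 describes proteinuria as "confirmed by doubling in the urinary albumin-creatinine ratio (ACR) or urinary protein-creatinine ratio (PCR) (if applicable"). Whether that matters is taken up under the objection.

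**The case against.** The strongest reply is that the mismatch in the text is certain but a gap in practice is not. Section 6.5.4 leaves collection and reporting details to a laboratory manual that is not among the documents, and the central laboratory's strip may well report glucose. That stands as a limit on the conclusion. It does not remove the inconsistency: if the manual includes glucose, the protocol's list is wrong and should be corrected.

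It can also be said that plasma glucose and HbA1c are already monitored, that glycosuria is not among the drug risks named in Section 3.6, and that Section 11 allows extra safety assessments case by case. All of this is true, and it keeps the point small. None of it makes the alert work, because blood glucose appears in Table 15-1 as a response to glycosuria and not as its trigger.

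Three stronger readings are tempting, and the documents do not support them.

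- A reader might infer that patients with glycosuria and normal blood glucose are the group being missed. Table 15-1 does not say the row is aimed at them. Its first step, a fasting blood glucose, fits a check for unrecognized hyperglycemia equally well.
- A reader might infer that renal monitoring as a whole is compromised. Two of the three urine alerts and all the serum rules have scheduled inputs.
- A reader might infer that the missing baseline ratio disables the proteinuria rule. Section 7.4 makes ratio confirmation conditional. Table 15-1 already tells sites to "Confirm value after 24 to 48h" for new dipstick proteinuria, and the two pre-dose dipsticks show whether it is new. An event can be closed by creatinine within 10% of baseline or by "protein-creatinine ratio within 50% of baseline", or by stabilization instead. Baseline creatinine is scheduled, so the absent ratio blocks nothing. Taken literally, that choice already lets a urine event with unchanged creatinine close at once, but the missing ratio is not the cause.

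**Conclusion.** Wrong as written, and minor. One of three urine alerts has no scheduled input, at 0 of 4 urinalysis visits. The conclusion rests on reading the dipstick list in Section 6.5.4.4 as complete and on the protocol text alone. If the laboratory manual already includes glucose, what remains is a wording error. The consequence is confined to safety monitoring, and no count of missed events is claimed because the documents give no glycosuria rate. The absence of a scheduled baseline ratio is worth noting, but it does not call for a change to the proteinuria confirmation or resolution rules.

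**What to change.** Choose one of two changes.

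- **Keep the alert.** Add glucose to the dipstick list in Section 6.5.4.4, on the urine already collected at Visits 1, 101, 105 and 199/PSD. Including the two pre-dose visits matters, because they show whether a later positive is new. If the laboratory manual already has glucose, simply correct the list to match.
- **Drop the alert.** Delete glycosuria from Section 7.4 and its row from Table 15-1.

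The first option costs one analyte and a line of text, with no new visit or sample. Its downside is some extra glycosuria results to review, although Table 15-1 already sets aside those due to diabetes. The second costs only wording and gives up the signal. The proteinuria rules and the SAP need no change under either.
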